## 15.5. Change of Dosing Regimen and Analysis

If clinically indicated, the participant and investigator, based on the participant-reported reason for the request and physical examination, can jointly decide to return the participant to QW dosing during the maintenance dosing period. Participants who switch back to QW dosing will not be allowed to switch back to Q2W dosing during the study.

The number and percentage of participants on Q2W and QW dosing will be summarized by visit for the SAF, number and percentage of participants switch from Q2W to QW at any time will also be summarized by parent study treatment

Document: BIOSdata\argenx\Efgartigimod\HAB40220\Biostatistics\Documentation\SAP

Author: Version Number: 1.0

Version Date: 03 June 2024

Template No.: CS\_TP\_BS016 Revision 7 Reference: CS\_WI\_BS005

Page 46 of 54

arm.

Summary statistics will be provided for time from first infusion to switch back to QW dosing for FAS. A Kaplan-Meier plot for the time to switch back to QW will also be provided by parent study treatment arm, the number of subjects at risk at each timepoint and probability of staying on Q2W will be presented. Subjects that do not enter the maintenance dosing period will not be included in this analysis.

The definition of events and censoring:

- Subjects in maintenance dosing period (Q2W for 42 weeks) switch back to QW will be the event.
- If subject does not have the event up to the end of study, the subject will be censored at the date of whichever occurs first, the last dose date or cut-off date.

#### 15.5.1. Derivations

• Time from first infusion to switch back to QW dosing (days) = date of first IMP administration – date of first switch back to QW dosing administration + 1.

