## 9.3.3.6. Change of Dosing Regimen and Analysis

Counts by visit will be presented of numbers and proportions on Q2W and QW dosing.

The temporal relationship between dosing regimen and both efficacy and safety will be explored and displayed visually.

COMPASS 31 efficacy score will be presented by visit for 2 subgroups, where the subgroups are defined as changing back at any time from Q2W to QW dosing regimen (Y/N).

Further exploratory analysis by dosing regimen may be performed.

Time from first infusion to switch back to QW dosing will be analyzed and a Kaplan-Meier plot of probability of staying on Q2W will be presented.

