### 3. STUDY DESIGN

## 3.1. General Description

Study ARGX-113-2105 (2105) is a long-term, single-arm, open-label, multicenter extension of the ARGX-113-2104 (2104) study, designed to evaluate the long-term safety of efgartigimod IV in adult patients with PC-POTS. Participants will be enrolled from both active and placebo arms of the 2104 study and will receive efgartigimod IV 10 mg/kg in the extension study without knowledge of their prior treatment arm. To be eligible to enroll in this study, participants must have completed the 24-week treatment period of the 2104 study and must not have permanently

Document: BIOSdata\argenx\Efgartigimod\HAB40220\Biostatistics\Documentation\SAP

Author: Version Number: 1.0

Version Date: 03 June 2024

Template No.: CS\_TP\_BS016 Revision 7 Reference: CS\_WI\_BS005

Page 13 of 54

discontinued the IMP in that study.

The treatment period of this study is 48 weeks. Participants will receive efgartigimod (10 mg/kg) by IV infusion QW for the first 4 weeks (induction dosing period), and then Q2W for 42 weeks (maintenance dosing period). Participants will return for a safety follow-up visit approximately 56 days after the last dose of IMP administration. The total study duration is approximately 386 days comprising:

- Treatment period of 48 weeks:
  - Induction dosing period: 4-week period of QW efgartigimod IV dosing from day 1 (baseline) to day 22 (week 3)
  - Maintenance dosing period: 42-week period from day 29 (week 4) to day 323 (week 46) Q2W. Participants will receive efgartigimod IV doses Q2W, with the first dose of this period administered on day 29 (week 4). If clinically indicated (e.g., the participant loses PC-POTS symptom control), the participant and investigator, based on the participant-reported reason for the request and physical examination, can jointly decide to return to QW dosing. Participants who switch back to QW dosing will not be allowed to switch back to Q2W dosing during the study. Participants who switch must attend an unscheduled visit. The decision to switch to QW dosing and the date of the switch should be recorded in the eCRF.
  - End of treatment visit on week 48.
- Safety follow-up period starting after last dose of IMP, with a safety follow-up visit approximately 56 days after the last dose of IMP administration.

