### Treatment and Dosing:

The treatment period of this study is 48 weeks. Participants will receive efgartigimod (10 mg/kg) by IV infusion QW for the first 4 weeks (induction dosing period), and then once Q2W for 44 weeks (maintenance dosing period).

Efgartigimod will be administered during the treatment period in an approximately 1-hour IV infusion by site staff or a home nurse. If clinically indicated (e.g., the participant loses PC-POTS symptom control), the participant and investigator, based on the participant-reported reason for the request and physical examination, can jointly decide to return the participant to QW dosing during the maintenance dosing period. Participants who switch back to QW dosing

Document: BIOSdata\argenx\Efgartigimod\HAB40220\Biostatistics\Documentation\SAP

1.0 Author: Version Number:

> Version Date: 03 June 2024

Template No.: CS\_TP\_BS016 Revision 7 Reference: CS WI BS005

Page 14 of 54

will not be allowed to switch back to Q2W dosing during the study. Participants who switch must attend an unscheduled visit.

The decision to switch to QW dosing and the date of the switch should be recorded in the eCRF. The final dose for participants who remain on Q2W dosing will be administered at week 46 (day 323). The final dose for participants who switch back to QW dosing during the maintenance dosing period will be administered at week 47 (day 330). The end of treatment visit occurs on week 48 (day 337).

[figure not shown]
The 10 mg/kg efgartigimod dose is based on body weight, and the maximum total dose per efgartigimod infusion is 1200 mg for participants who weigh ≥120 kg. The dose level will be recalculated if a participant's weight has changed (increased or decreased) by more than 10% from baseline. Otherwise, dose modifications are not permitted.

IMP infusions must occur at the site for a minimum of 3 consecutive visits (baseline visit and the week 1 and 2 visits) before home infusions are allowed. If doses are missed at 1 or more of these visits, then dosing at subsequent visits will also be on-site. IMP administration at home will not commence until after 3 doses have been administered onsite.

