## 6. GENERAL CONSIDERATIONS

## 6.1. Reference Start Date and Study Day

Study Day will be calculated from the reference start date and will be used to show start/stop day of assessments and events. It will appear in every listing where an assessment date or event date appears.

- Reference start date is defined as the day of the first dose of IMP.
- If the date of the event is on or after the reference date, then:
  - Study Day = (date of event reference date) + 1.
- If the date of the event is prior to the reference date, then:
  - Study Day = (date of event reference date).

In the situation where the event date is partial or missing, the date will appear partial or missing in the listings, and Study Day. Date implies a complete date having day, month and year available. Unless otherwise specified, the study day will remain missing when it cannot be calculated due to absence or incompleteness of the concerned and/or reference dates.

In case the participant never received IMP, the date/time of informed consent will be used instead of first IMP administration date/time.

End of study (EOS) is defined as date of participant's last visit. This is date of treatment period completion and/or safety follow-up or early discontinuation visit.

End of treatment (EOT) is defined as date of treatment completion or date of permanent discontinuation of IMP.

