#### 14.1. **Adverse Events**

AEs and SAEs will be collected as defined in the section 10.3 of the protocol. Refer to the criteria in Appendix 1 for which AEs collects in POTS will be added into POTS-OLE. AEs will be coded using latest version of Medical Dictionary for Regulatory Activities (MedDRA) central coding dictionary. AEs will be graded using the National Cancer Institute (NCI) Common Terminology Criteria for Adverse Events (CTCAE) version 5.0. For each AE, start and stop date/times are collected as well as severity, a seriousness flag, treatment-relatedness, relatedness to procedures, action taken towards the study drug and outcome.

Treatment-emergent adverse events (TEAEs) are defined as AEs with onset on or after the first administration of IMP in this 2105 study up to and including 60 days after the last IMP administration before the event (refer to schematic).

D1: IMP start	D40: Start IMP interruption		D120: IMP restart	D160: Start IMP disc			D240: Study disc		
IMP					IMP				
TE: D1-D40	TE: days	D40+60	Non-TE: 119	D101-	TE:D120-D160	TE: days	D160+60	Non-TE: >D220	

AEs will be considered treatment-emergent based on their start date/time. If the AE start date/time is incomplete or missing, the AE will be considered treatment-emergent unless the available part of the AE start or stop date/time

Document: BIOSdata\argenx\Efgartigimod\HAB40220\Biostatistics\Documentation\SAP

1.0 Version Number: Author:

> Version Date: 03 June 2024

Template No.: CS\_TP\_BS016 Revision 7 Reference: CS\_WI\_BS005

Page 30 of 54

provide evidence that the event did not occur within 60 days from last IMP administration before the event.

AE onset and duration will be calculated as follows when start and stop dates are fully known: AE onset day (vs. first administration)

- $\circ$  AE start date  $\geq$  date of first administration: AE start date date of first administration + 1 day
- AE start date < date of first administration: AE start date date of first administration
- AE duration (days) =
- AE end date -AE start date +1 day
- Study discontinuation date =
- AE start date + 1 day (when the AE start date is fully known but the AE is not resolved at the end of the study). In this case the duration will be presented as ">x days".

An AE for which the study drug was discontinued is defined as an AE with action taken "drug withdrawn".

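### SAP 15.5.1 subtracts the switch date from the first-infusion date, so every time to switch back to QW dosing comes out negative

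*SAP*

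**What the plan says.** Protocol 9.3.3.6 pre-specifies the analysis: "Time from first infusion to switch back to QW dosing will be analyzed", with a Kaplan-Meier plot of the probability of remaining on Q2W. SAP 15.5 takes this up: "Summary statistics will be provided for time from first infusion to switch back to QW dosing for FAS". It adds a Kaplan-Meier plot by parent-study arm and leaves out participants who never reach the maintenance period. The event is a switch to QW during maintenance. Participants without the event are "censored at the date of whichever occurs first, the last dose date or cut-off date".

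SAP 15.5.1 then gives the only formula for the variable, in days: "date of first IMP administration – date of first switch back to QW dosing administration + 1".

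Two other places in the SAP show how it normally counts days. In SAP 6.1, "Reference start date is defined as the day of the first dose of IMP", and events on or after that date are counted forward from it with 1 added. In SAP 14.1, the duration of an adverse event is "AE end date -AE start date +1 day", that is, later date minus earlier date plus 1.

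**The concern.** A duration from first infusion to switch should be the switch date minus the infusion date, plus 1 if day 1 is the day of first infusion. SAP 15.5.1 has the two dates the other way round. Followed as written, it produces negative times that rank late switchers before early ones. A Kaplan-Meier curve cannot be drawn from such times, and summary statistics of them have no meaning.

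There is also a quieter risk. Someone who sees the negative sign and simply removes it gets times that look plausible but are 2 days too short. SAP 15.5 gives the censoring date but no formula for the censored time. If censored times follow the Study Day convention while event times are 2 days short, the two are on different scales and some risk sets change.

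**Working it through.** The plan states no numerical result for this variable, so there is no figure to reproduce. The check is date arithmetic.

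**Inputs**
- Time origin: the first IMP dose is Study Day 1 (SAP 6.1).
- Earliest possible event: the maintenance period starts on day 29 (SAP 3.1). The day 29 dose is itself the first Q2W maintenance dose, so day 29 is an outer bound. The first nominal dose that departs from the Q2W schedule is at week 5, day 36 (protocol 1.3, Table 1).
- Latest possible event: the final QW dose after a switch is on day 330 (SAP 3.1, Treatment and Dosing).
- Visit window: ±2 days (protocol 1.3, Table 1).

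**Formulas**

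Let R be the date of the first infusion. A switch on Study Day d then has date R + (d − 1).
- As written: R − [R + (d − 1)] + 1 = 2 − d.
- With the dates swapped: [R + (d − 1)] − R + 1 = d.
- Error: d − (2 − d) = 2d − 2 days.
- As written, with the sign dropped: |2 − d| = d − 2, which is 2 days short for every switch.

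**Results**

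| Switch on day d | As written (2 − d) | Dates swapped (d) | Error (2d − 2) | Sign dropped (d − 2) |
|---|---|---|---|---|
| 29 | −27 | 29 | 56 | 27 |
| 36 | −34 | 36 | 70 | 34 |
| 169 | −167 | 169 | 336 | 167 |
| 330 | −328 | 330 | 658 | 328 |

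The written rule gives zero or a positive value only for d = 2 or d = 1. Neither can occur, because the event requires entry into maintenance. With the ±2-day window, d runs from 27 to 332. Evaluated with calendar dates for every d in that range, the rule is negative throughout (−25 to −330).

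**Effect on the summaries.** For illustration, assume four switches on days 36, 100, 200 and 330 (the documents give no such data). The correct mean is (36 + 100 + 200 + 330)/4 = 166.5, the median is (100 + 200)/2 = 150, and the range is 36 to 330. The written rule gives a mean of 2 − 166.5 = −164.5, a median of 2 − 150 = −148, and a range of −328 to −34.

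**Effect of dropping the sign.** A switch on day 120 becomes 118. If another participant is censored at day 119 on the Study Day scale, the event now falls before the censoring instead of after it, and that participant is wrongly counted as at risk.

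**The case against.** The strongest reply is that this is a transposition that can mislead nobody. The label on the same line of SAP 15.5.1 runs from first infusion to switch, and protocol 9.3.3.6 and SAP 15.5 use the same phrase, so the intended direction is not in doubt. A column of negative times would be noticed at once in a table or plot, and the 2-day error arises only if someone sees the sign and then patches it wrongly. The study tests no hypothesis and its results are not used inferentially. The counts on Q2W and QW by visit, the proportion who ever switch, and the COMPASS 31 and MaPS subgroups by switch status do not use this formula.

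All of that stands, and it limits the weight of the point. It does not make the formula right. Loss of characters in the PDF text does not explain the error either: the minus sign is present, and a lost character could not exchange two dates. No other section of the protocol or SAP gives a corrected formula.

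**Conclusion.** The formula is wrong as written. Every switch time that the plan allows becomes negative and the order of switchers is reversed. The nominal range is −34 to −328 if the first QW dose after a switch falls on day 36 at the earliest, or −27 to −328 if day 29 is taken as an outer bound. The corresponding errors are 70 to 658 days, or 56 to 658 days. This assumes that the rule is programmed literally and that the first infusion is Study Day 1, as SAP 6.1 states.

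The point is minor. It affects one descriptive variable and the two outputs built on it, the intent can be recovered from the SAP itself, and a programmer would probably notice.

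**What to change.** In SAP 15.5.1, reverse the two dates and give the censored time explicitly:

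- Event time (days) = date of the first QW infusion after the switch − date of the first IMP infusion + 1.
- Censored time (days) = censoring date under SAP 15.5 − date of the first IMP infusion + 1.

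Add a reference to SAP 6.1, so that both times are Study Days. The cost is a few words in the SAP. Data collection, visits, dosing and the event and censoring definitions stay as they are.

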#### 16. EXPLORATORY ANAYSIS

The exploratory efficacy analyses and QoL will be performed for the FAS.

Summary statistics will be provided in terms of absolute value and changes from baseline for each visit.

16.1.			
		_	
16.2.			

Document: BIOSdata\argenx\Efgartigimod\HAB40220\Biostatistics\Documentation\SAP

Author: Version Number: 1.0

Version Date: 03 June 2024

Template No.: CS\_TP\_BS016 Revision 7 Reference: CS\_WI\_BS005

Page 47 of 54

**16.3. 16.4.** 16.5. Document: BIOSdata\argenx\Efgartigimod\HAB40220\Biostatistics\Documentation\SAP

Template No.: CS\_TP\_BS016 Revision 7

Reference: CS\_WI\_BS005

Version Number: Version Date: 1.0

03 June 2024

Effective Date: 01Nov2021

Author:

Page 48 of 54

#### APPENDIX 1. Programming Conventions for Outputs

### **IQVIA Output Conventions**

Outputs will be presented according IQVIA Standard conventions. Kindly refer to output templates for additional information.

#### **Dates & Times**

Depending on data available, dates and times will take the form yyyy-mm-ddThh:mm:ss.

## **Presentation of Treatment Groups**

For outputs, treatment groups will be represented as follows and in the given order:

Treatment Group for Tables, Listings and Figures
Efgartigimod

In the general characteristics analysis, an overall total will be added to summarize all participants over subgroups. Overall totals will be shown last.

## Listings

All listings will be ordered by the following (unless otherwise indicated in the template):

- Treatment group (or treatment received if it's a safety output)
- Center-participant ID,
- Date (where applicable),

For listings where non-enrolled participants are included, these will appear in a category after the enrolled treatment groups labeled 'Not Randomized'.

#### **Baseline**

Baseline for these data will integrate from the latest non-missing data of 2104 to baseline visit of 2105.

Description		Source
	 	

Document: BIOSdata\argenx\Efgartigimod\HAB40220\Biostatistics\Documentation\SAP

Author: Version Number: 1.0

Version Date: 03 June 2024

Template No.: CS\_TP\_BS016 Revision 7 Reference: CS\_WI\_BS005

Effective Date: 01Nov2021

Copyright © 2009, 2010, 2012, 2016, 2018, 2019, 2021 IQVIA. All rights reserved. The contents of this document are confidential and proprietary to IQVIA Holdings Inc. and its subsidiaries. Unauthorized use, disclosure or reproduction is strictly prohibited.

Page 50 of 54

Physical Examination	EDC data: PE1
ECG	EDC data: EG
	Non-EDC data: ECG
Laboratory Assessment - Hematology and Chemistry	EDC data: LB
	Non-EDC data: Q  S (and RBM)
Laboratory Assessment: Immunogenicity Sample	EDC data: LB_IMMUNO
	Non-EDC data: Q  S (and RBM)
Laboratory Assessment: Biomarker Sample	EDC data: LB_MI_BIO
	Non-EDC data: Q  S (and RBM)
Lab Page - Urinalysis	EDC data: LB1
	Non-EDC data: Q  S (and RBM)
Lab Page - TSH/CRP/ESR	EDC data: LB2
	Non-EDC data: Q  S (and RBM)
Pharmacokinetics Concentration	EDC data: PC1
	Non-EDC data: PK
Pharmacodynamics	EDC data: PD
	Non-EDC data: Q  S (and RBM)
Pregnancy Testing	EDC data: PREG
ADA	Non-EDC data: ADA
eCOA	Non-EDC data: eCOA

#### Baseline for these data will use 2105 baseline data

Description	Source
Vital Sign	EDC data: VS
Adverse Events	EDC data: AE
Prior and Concomitant Medications	EDC data: CM
Medical History	EDC data: MH
Date of Visit	EDC data: VIS
Study Continuation	EDC data: STDYCON
Pandemic Visit Impact	EDC data: VIS_PAND
IRT	Non-EDC data: IRT

# Criterias of prior/concomitant medications, Medical history and AEs from POTS to POTS-OLE

POTS Form	Criteria when met in POTS, the respective record will be added into
	POTS-OLE
Adverse Event (Eg. HEADACHE)	Outcome = Recovering/Resolving or Not Recovered/Not Resolved or Unknown     Prior and Concomitant Medications = Ongoing with Indication = Adverse Event (HEADACHE)

Document: BIOSdata\argenx\Efgartigimod\HAB40220\Biostatistics\Documentation\SAP

Author: Version Number: 1.0

Version Date: 03 June 2024

Template No.: CS\_TP\_BS016 Revision 7 Reference: CS\_WI\_BS005

Simple to the second se

Page 51 of 54

Medical History (Eg. HEADACHE)	Ongoing     Prior and Concomitant Medications = Ongoing with Indication = Medical History (HEADACHE)
Related Procedures/Surgeries (Eg. Cataract extraction)	Ongoing     Prior and Concomitant Medications = Ongoing with Indication = Related Procedures/Surgeries (Cataract extraction)
Prior and Concomitant Medications	Ongoing

Document: BIOSdata\argenx\Efgartigimod\HAB40220\Biostatistics\Documentation\SAP

Author: Version Number: 1.0

Version Date: 03 June 2024

Template No.: CS\_TP\_BS016 Revision 7 Reference: CS\_WI\_BS005

## **APPENDIX 2. TOXICITY GRADES**

The table below shows how the CTCAE, v5.0: 27 Nov 2017 will be implemented in the analysis.

Paramater	Unit	Grade 1	Grade 2	Grade 3	Grade 4
Alanine amino transferase		>1-3 *ULN	>3-5 *ULN	>5-20 *ULN	>20 *ULN
Albumin	g/L	<lln-30< td=""><30-20	<20	-	</lln-30<>	<30-20	<20	-
	g/dL	<lln-3< td=""><3-2	<2	-	</lln-3<>	<3-2	<2	-
Alkaline phosphatase		>1.0-2.5 *ULN	>2.5-5.0 *ULN	>5.0-20.0 *ULN	>20.0 *ULN
Aspartate amino transferase		>1-3 *ULN	>3-5 *ULN	>5-20 *ULN	>20 *ULN
Bilirubin (total)		>1.0-1.5 *ULN	>1.5-3.0 *ULN	>3.0-10.0 *ULN	>10.0 *ULN
Calcium (ionized) low	mmol/L	<lln-1.0< td=""><1.0-0.9	<0.9-0.8	<0.8	</lln-1.0<>	<1.0-0.9	<0.9-0.8	<0.8
	mg/dL	<lln-4.0< td=""><4.0-3.6	<3.6-3.2	<3.2	</lln-4.0<>	<4.0-3.6	<3.6-3.2	<3.2
Calcium (ionized) high	mmol/L	>ULN-1.5	>1.5-1.6	>1.6-1.8	>1.8
	mg/dL	>ULN-6.0	>6.0-6.4	>6.4-7.2	>7.2
Calcium (corrected)	mmol/L	<lln-2.00< td=""><2.00-1.75	<1.75-1.50	<1.50	</lln-2.00<>	<2.00-1.75	<1.75-1.50	<1.50
low	mg/dL	<lln-8< td=""><8-7	<7-6	<6	</lln-8<>	<8-7	<7-6	<6
Calcium (corrected)	mmol/L	>ULN-2.9	>2.9-3.1	>3.1-3.4	>3.4
high	mg/dL	>ULN-11.5	>11.5-12.5	>12.5-13.5	>13.5
Creatinine		>1.0-1.5 *ULN	>1.5-3.0 *ULN	>3.0-6.0 *ULN	>6.0 *ULN
Glucose (fasting) low	mmol/L	<lln-3.0< td=""><3.0-2.2	<2.2-1.7	<1.7	</lln-3.0<>	<3.0-2.2	<2.2-1.7	<1.7
Potassium low	mmol/L	-	<lln-3.0< td=""><3.0-2.5	<2.5	</lln-3.0<>	<3.0-2.5	<2.5
	mEq/L	-	<lln-3.0< td=""><3.0-2.5	<2.5	</lln-3.0<>	<3.0-2.5	<2.5
Potassium high	mmol/L	>ULN-5.5	>5.5-6.0	>6.0-7.0	>7.0
	mEq/L	>ULN-5.5	>5.5-6.0	>6.0-7.0	>7.0

Document: BIOSdata\argenx\Efgartigimod\HAB40220\Biostatistics\Documentation\SAP

Author: Version Number: 1.0

Version Date: 03 June 2024

Template No.: CS\_TP\_BS016 Revision 7 Reference: CS\_WI\_BS005

Page 53 of 54

Paramater	Unit	Grade 1	Grade 2	Grade 3	Grade 4
Sodium low	mmol/L	<lln-130< td="">-	<130-120	<120	</lln-130<>	-	<130-120	<120
	mEq/L	<lln-130< td="">-	<130-120	<120	</lln-130<>	-	<130-120	<120
Sodium high	mmol/L	>ULN-150	>150-155	>155-160	>160
	mEq/L	>ULN-150	>150-155	>155-160	>160
Lymphocytes (absolute	giga/L	<lln-0.80< td=""><0.80-0.50	<0.50-0.20	<0.20	</lln-0.80<>	<0.80-0.50	<0.50-0.20	<0.20
count) low	counts/mm 	<lln-800< td=""><800-500	<500-200	<200	</lln-800<>	<800-500	<500-200	<200
Lymphocytes (absolute	giga/L	-	>4-20	>20	-
count) high	counts/mm 	-	>4000-20000	>20000	-
Neutrophils (absolute	giga/L	<lln-1.5< td=""><1.5-1.0	<1.0-0.5	<0.5	</lln-1.5<>	<1.5-1.0	<1.0-0.5	<0.5
count) low	counts/mm 	<lln-1500< td=""><1500-1000	<1000-500	<500	</lln-1500<>	<1500-1000	<1000-500	<500
Platelets	giga/L	<lln-75< td=""><75-50	<50-25	<25	</lln-75<>	<75-50	<50-25	<25
White blood cells	giga/L	<lln-3< td=""><3-2	<2-1	<1	</lln-3<>	<3-2	<2-1	<1
	counts/mm 	<lln-3000< td=""><3000-2000	<2000-1000	<1000	</lln-3000<>	<3000-2000	<2000-1000	<1000

CTCAE= Common Terminology Criteria for Adverse Events; LLN=lower limit of normal; ULN=upper limit of normal , values within normal ranges will be presented as Grade 0 for toxicity outputs.

Note: In case ULN/LLN is higher/lower than the upper/lower limit of grade 1 (or even higher grades), ULN/LLN will be ignored and only the fixed values of CTCAE will be considered.

Document: BIOSdata\argenx\Efgartigimod\HAB40220\Biostatistics\Documentation\SAP

Author: Version Number: 1.0

Version Date: 03 June 2024

Template No.: CS\_TP\_BS016 Revision 7 Reference: CS\_WI\_BS005

